10.4.3 ANALYSIS OF THE SECONDARY ENDPOINT(S)

Comparisons of values for the binary secondary endpoints of target weight achievement, patient acceptance, and symptom occurrence between HD treatments will be performed using generalized estimating equations. Comparisons of values for the continuous secondary endpoints of pre-HD to nadir intradialytic HD systolic BP change, intradialytic nadir systolic BP change, target and post-HD weight difference, and TTE ejection fraction change will be performed using ANOVA or non-parametric methods depending on data type.

10.4.4 SAFETY ANALYSES

See “8.6. Safety Oversight.” The primary safety endpoint that will be monitored is BP but all AEs and SAEs will be evaluated for safety concerns.

10.4.5 ADHERENCE AND RETENTION ANALYSES

Adherence and retention will be analyzed on a weekly basis by the PI and study coordinator throughout the course of the study.

10.4.6 BASELINE DESCRIPTIVE STATISTICS

Baseline patient characteristics will be reported as counts and proportions for categorical variables, and as means and standard deviations or medians and inter-quartile ranges for continuous variables.

10.4.7 PLANNED INTERIM ANALYSES

10.4.7.1 SAFETY REVIEW

See “8.6. Safety Oversight.” This will be performed on an ongoing basis throughout the course of the study by 2 nephrologists not associated with the study. There will be 2 formal interim statistical analyses of nadir systolic BP and pre- to post-dialysis BP change across the trial arms: 1) after 10 participants have completed 2 phases of the study (1 conventional and 1 UF profiling phase) and 2) after 20 participants have completed 2 phases of the study (1 conventional and 1 UF profiling phase). Statistical rules will not be used to halt study enrollment.

10.4.7.2 EFFICACY REVIEW

Efficacy review will be performed at the completion of the study or at the time of termination if the study is terminated early.

10.4.8 ADDITIONAL SUB-GROUP ANALYSES

N/A

10.4.9 MULTIPLE COMPARISON/MULTIPLICITY

There are 3 primary outcomes. Analyses will be performed with and without correction for multiple testing. The Bonferroni correction will be used to adjust confidence intervals to decrease type 1 error when adjusting for multiple testing.

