10.4 DESCRIPTION OF STATISTICAL METHODS

10.4.1 GENERAL APPROACH

By cross-over design, each participant will act as his or her own control, permitting between and within group comparisons. Analyses will be performed on an intention-to-treat and modified intention-to-treat basis, separately. Comparisons of values between HD treatments will be performed by repeated-measures analysis of variance (ANOVA; or non-parametric methods depending on data type) for continuous outcomes and generalized estimating equations for categorical outcomes. Analogous analyses will be performed in both the intention-to-treat and modified intention-to-treat datasets. All statistical estimates will be tabulated along with their corresponding 95% confidence intervals. All reported P values will be 2-sided; <0.05 representing significance. All hypothesis tests that are observed to be statistically non-significant will be interpreted as such and reported as being inconclusive. However, as this is a small, pilot study, the magnitude of estimates and the corresponding confidence intervals will be considered in the results interpretation.

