10.5 SAMPLE SIZE

This cross-over study is designed as a pilot study to test for efficacy signals. However, with its cross-over design in which each participant acts as his or her own control, we are powered to detect clinically and statistically significant differences across arms within patients. With a sample size of 30, we have 80% power to detect a 5.9 mmHg difference in nadir SBP (S.D. 8), a ≥ 0.07 ng/mL troponin T difference (S.D. 0.1), a 2.2% strain difference (S.D. 3), and 4% ejection fraction difference (S.D. 5); all clinically meaningful differences. We have 80% power to detect a 31% absolute difference in the binary endpoint of Troponin T change >0.1 ng/mL (event rate=20%).

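### Optional improvement: use Holm for the multiplicity-corrected tests of the three primary outcomes and keep the Bonferroni intervals for display

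*Combined protocol and SAP*

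**What the plan says.** Protocol section 10.4.9 states "There are 3 primary outcomes" and continues "Analyses will be performed with and without correction for multiple testing". The corrected version is described in one sentence: "The Bonferroni correction will be used to adjust confidence intervals to decrease type 1 error when adjusting for multiple testing". With three outcomes this means 0.05/3 each. The section gives no separate rule for corrected P values and does not say whether the corrected or the uncorrected result decides. The SAP does not mention multiplicity, so 10.4.9 is the whole of the plan's family-wise error control.

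Section 10.4.1 sets the general rule, "All reported P values will be 2-sided; <0.05 representing significance", and treats non-significant tests as inconclusive. It also gives intervals a leading role: "All statistical estimates will be tabulated along with their corresponding 95% confidence intervals". Because the trial is a small pilot, "the magnitude of estimates and the corresponding confidence intervals will be considered in the results interpretation".

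Section 10.5 gives detectable differences at 80% power with 30 participants. For strain, a primary outcome, it states "a 2.2% strain difference (S.D. 3").

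**The concern.** Single-step Bonferroni holds each primary outcome to 0.0167 whatever the other two show. A primary with a P value between 0.0167 and 0.05 is therefore inconclusive in the corrected analysis, even if both of the others succeed clearly. Holm can recover some of these results without relaxing the 5% bound.

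This trial is a natural place for it. Section 10.2 hypothesizes benefit on all three primaries, which is the case in which Holm gains most. Section 2.1 gives a shared mechanism running from hypoperfusion to hypotension, stunning and troponin release, so correlated endpoints are plausible, and Holm is valid under any correlation. What is at stake is power in the corrected analysis of a 30-patient trial, not the validity of its conclusions.

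**Working it through.** **Inputs.** Three primary outcomes (10.4.9); two-sided 0.05 (10.4.1); 30 participants, strain difference 2.2%, SD 3, 80% power (10.5). Two things are assumed because the documents do not give them: every real effect has 80% power at unadjusted 0.05, and the correlation between test statistics lies between 0 and 0.8.

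**1. Reproduce the plan's figure.** Treat strain as a comparison of two means with 30 observations per condition. The noncentrality is 2.2 / (3 × √(2/30)) = 2.840. The critical t on 58 df is 2.002 at 0.05, giving power of 79.8%. The stated 80% is therefore reproduced at unadjusted alpha. At 0.05/3 the critical t is 2.465 and power is 64.7%.

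**2. Bonferroni in general terms.** 0.05/3 = 0.0167, so the corrected intervals are 98.33% intervals. Their multiplier is 2.394 against 1.960, which makes them 22% wider. An effect with 80% power has a mean test statistic of 1.960 + 0.842 = 2.802. Its power is:
- at 0.0167: Φ(2.802 − 2.394) = 65.8%
- at 0.025: Φ(2.802 − 2.241) = 71.2%
- at 0.05: 80.0%

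**3. Holm, all three effects real, independent.** The ordered P values are compared with 0.0167, 0.025 and 0.05, stopping at the first failure. Let a = 0.6582 be the chance that P is at most 0.0167, b = 0.7123 − 0.6582 = 0.0541 the chance that it lies between 0.0167 and 0.025, c = 0.8000 − 0.7123 = 0.0877 between 0.025 and 0.05, and d = 1 − 0.7123 = 0.2877 above 0.025.
- At least one rejection: 1 − (1 − a)³ = 0.960, the same as Bonferroni.
- At least two: a³ + 3a²b + 3a²d + 3ab² + 6abd = 0.797.
- All three: a³ + 3a²b + 3a²c + 3ab² + 6abc = 0.285 + 0.070 + 0.114 + 0.006 + 0.019 = 0.494. Bonferroni gives a³ = 0.285.
- Per endpoint: (0.960 + 0.797 + 0.494)/3 = 0.750. Bonferroni gives 0.658.

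**4. Other scenarios.** Simulation of 1,000,000 trials per scenario, three normal test statistics:

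| Quantity | Bonferroni | Holm |
|---|---|---|
| Per endpoint, three real, correlation 0 | 65.8% | 75.1% |
| Per endpoint, three real, correlation 0.8 | 65.8% | 72.4% |
| Per endpoint, two real, correlation 0.8 to 0 | 65.8% | about 69–70% |
| Per endpoint, one real, correlation 0.8 to 0 | 65.8% | 65.9–66.0% |
| All three significant, three real, correlation 0 | 28.6% | 49.5% |
| All three significant, three real, correlation 0.8 | 51.3% | 65.9% |
| At least one significant, three real, correlation 0 | 96.0% | 96.0% |
| At least one significant, three real, correlation 0.8 | 79.5% | 79.5% |

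**5. Error rate.** Holm's family-wise error was at most 0.049 in every scenario. Within the bound it can be higher than Bonferroni's: with two real effects and correlation 0 it is 3.65% against 1.65%.

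**6. Tests against intervals.** Take illustrative P values of 0.001, 0.010 and 0.030. Holm rejects all three (0.001 ≤ 0.0167, 0.010 ≤ 0.025, 0.030 ≤ 0.05). The third outcome's 98.33% interval still includes no effect, because 0.030 is above 0.0167.

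**The case against.** The strongest objection is that 10.4.9 applies Bonferroni to confidence intervals, and 10.4.1 leans on intervals for interpretation. Bonferroni yields simultaneous intervals directly. Holm is a P-value procedure without simple matching intervals. This stands, and it is why the intervals should stay as they are and Holm should be confined to the corrected significance decisions.

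A reader might infer that Holm comes at no cost, that Bonferroni is a mistake here, or that each primary is finally judged only at 0.05/3. The documents support none of these. The mismatch in step 6 is a real cost in a plan that reads its results through intervals. Bonferroni is prespecified, valid and conservative. Uncorrected results are reported beside the corrected ones in a trial that calls itself a pilot, so no single binding rule is set. Holm does not settle which version decides.

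The size of the gain is also open to challenge. The 80% figure is anchored in the protocol for strain only. Nadir systolic BP, also listed in 10.5, is a secondary endpoint. No power is given for the hypotension primary. The binary troponin figure uses a change above 0.1 ng/mL, not the rise of at least 10% analysed in 10.4.2. If the strain SD of 3 were the SD of within-patient differences, a paired t-test would have noncentrality 2.2 / (3/√30) = 4.017 and power of 97.3% at 0.05 and 92.2% at 0.0167. With all three endpoints at that level and independent, Holm would give 96.9%, a gain of about 5 points instead of 9. Finally, no section requires all three primaries to be significant, so the contrast of 29% with 49% is the most favourable way to show the benefit.

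**Conclusion.** The point holds as a cheap, optional improvement. For the corrected tests Holm never rejects less than Bonferroni and keeps the 5% family-wise bound under any correlation. Under the assumed 80% power per real effect, the gain per endpoint is about 7 to 9 points if all three effects are real, about 3 to 4 if two are, and essentially nil if one is. It would be smaller if true power is higher. The chance of at least one significant primary does not change.

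**What to change.** In 10.4.9, add one sentence: the multiplicity-corrected significance decisions for the three primary outcomes use Holm's procedure (ordered P values against 0.0167, 0.025 and 0.05), the Bonferroni-adjusted 98.33% intervals remain the displayed simultaneous intervals, and the two may disagree. Repeat it in the SAP, and fix it before unblinding.

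No extra patients or data are needed. The costs are a line of explanation whenever an outcome is significant under Holm while its displayed interval includes no effect, and some of the slack that Bonferroni leaves below the 5% bound.

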10.4.10 TABULATION OF INDIVIDUAL RESPONSE DATA

Individual data will not be collected and stored by individual measure and timepoint, but individual data will not be publicly reported in this manner (reported only in aggregate).

10.4.11 EXPLORATORY ANALYSES

Comparisons of values for the continuous exploratory endpoints of early diastolic myocardial velocity change, tricuspid annulus systolic excursion velocity change, blood volume monitor slope change and plasma refill change will be performed using ANOVA or non-parametric methods depending on data type.

10.5 SAMPLE SIZE

This cross-over study is designed as a pilot study to test for efficacy signals. However, with its cross-over design in which each participant acts as his or her own control, we are powered to detect clinically and statistically significant differences across arms within patients. With a sample size of 30, we have 80% power to detect a 5.9 mmHg difference in nadir SBP (S.D. 8), a ≥ 0.07 ng/mL troponin T difference (S.D. 0.1), a 2.2% strain difference (S.D. 3), and 4% ejection fraction difference (S.D. 5); all clinically meaningful differences. We have 80% power to detect a 31% absolute difference in the binary endpoint of Troponin T change >0.1 ng/mL (event rate=20%).

10.6 MEASURES TO MINIMIZE BIAS

10.6.1 ENROLLMENT/ RANDOMIZATION/ MASKING PROCEDURES

Randomization assignments will be generated using computer-generated random numbers. Assignments will be sealed in envelopes prior to study start. After patients consent to study participation, sealed study arm assignments will be randomly allocated to experimental or control treatment for period 1. Sequence assignments will be sealed in envelopes prior to study start and opened in a predetermined order at the start of each study period. The study will be double-blinded in that patients will not be informed of the treatment paradigm. Investigators, including those performing TTE interpretation, will be blinded to treatment paradigm. Ultrasonographers performing intra-HD TTEs will be blinded to treatment paradigm.

10.6.2 EVALUATION OF SUCCESS OF BLINDING

At study close-out for each participant, we will assess blinding with qualitative questions regarding the participant's perception of the order of administered treatments.

10.6.3 BREAKING THE STUDY BLIND/PARTICIPANT CODE

The PI may only break the study code in an emergency (occurrence of an SAE where it is necessary for the PI or treating physician to know which treatment the patient is receiving before the participant can be treated) or at the end of the study. Breaking the study blinding/ participant code will be reported to the IRB.

11 SOURCE DOCUMENTS AND ACCESS TO SOURCE DATA/DOCUMENTS

Each participating site will maintain appropriate medical and research records for this trial, in compliance with ICH E6 and regulatory and institutional requirements for the protection of confidentiality of participants. As part of participating in a NIH IC-sponsored study, each site will permit authorized representatives of the NIH IC and regulatory agencies to examine (and when permitted by applicable law, to copy) clinical records for the purposes of quality assurance reviews, audits, and evaluation of the study safety, progress and data validity. Study staff will have access to study records.

Data (blood pressures, weights, dialysis treatment data) will be extracted from electronic medical records and stored in password-protected Excel flowsheets housed on a secure Department of Medicine server. Blood

volume monitor, treatment preference, and symptoms will be recorded on study data collection forms. TTE data will be downloaded from the TTE machine to secure Department of Medicine Servers, per standard protocols. All electronic information will be stored on a password-protected UNC server (with secure, password and firewall-protected Department of Medicine server back-up) and accessed via a UNC password-protected computer and will be identifiably by study identification number only. Information linking the study identification number to the patient will be kept in a separate, password-protected database on the server. Study charts will be maintained in a locked room of the dialysis clinic. Study charts will be identified by study IDs. Signed consent forms will be kept in a locked filing cabinet in the PI's locked office. Initial paper records of study HD treatment data, patient preferences and symptoms will be stored in the study chart and, after study completion, will be transferred to a locked filing cabinet in the locked office of the PI. Paper records will be destroyed (shredded and disposed in locked, shred bins) after verification of electronic data entry. Only the PI and research assistant will have access to patient information with patient identifiers.

12 QUALITY ASSURANCE AND QUALITY CONTROL

Quality control procedures will be implemented beginning with data entry system and data quality control checks that will be run on the database will be generated. Any missing data or data anomalies will be communicated to the site(s) for clarification/resolution. Following written SOPs, the monitors will verify that the clinical trial is conducted and data generated, documented (recorded), and reported in compliance with the protocol, GCP, and the applicable regulatory requirements. The investigational site will provide direct access to all trial-related sites, sources data/ documents, and reports for the purpose of monitoring and auditing by the sponsor, and inspection by local and regulatory authorities.

The PI will be responsible for quality assurance and quality control and will provide oversight of all research team members to assure adherence to the protocol. Except for in an emergency situation in which proper care for the protection, safety, and well-being of the study patient requires alternative treatment, the study shall be conducted exactly as described in the approved protocol.

13 ETHICS/PROTECTION OF HUMAN SUBJECTS

13.1 ETHICAL STANDARD

The investigators will adhere to NIH Human Research Protections Program policies and procedures.

13.2 INSTITUTIONAL REVIEW BOARD

It is expected that the IRB will have the proper representation and function in accordance with federally mandated regulations. The protocol, informed consent, recruitment materials and all participant materials will be submitted to the IRB for review and approval. Approval of both the protocol and the consent form must be obtained before any participant is enrolled. Any amendment to the protocol will require review and approval by the IRB before the changes are implemented in the study. All changes to the consent form will be IRB approved; a determination will be made regarding whether previously consented participants need to be re-consented. The investigators will adhere to NIH Human Research Protections Program policies and procedures.

13.3 INFORMED CONSENT PROCESS

13.3.1 CONSENT/ASSENT AND OTHER INFORMATIONAL DOCUMENTS PROVIDED TO PARTICIPANTS

An IRB-approved consent form and IRB-approved study informational page will be provided to potential participants.

13.3.2 CONSENT PROCEDURES AND DOCUMENTATION

In obtaining and documenting informed consent, the investigators will comply with the applicable regulatory requirement(s), and should adhere to Good Clinical Practice (GCP) Good Laboratory Practice (GLP) and to ethical principles that have their origin in the Declaration of Helsinki. The PI will approach eligible patients and offer them the opportunity to participate in the study. If the patient does desire to participate in the research study, informed consent will be obtained by the PI. The purpose of the informed consent procedure is to assist the patient in understanding the nature and purpose of the study and the risks and benefits of the study, to offer answers to questions about any details of the study, and to obtain the patient's signature on the IRB-approved consent form. All patients will be reminded that participation in the study is voluntary and that their medical care will not be affected if they choose not to participate. The patients will be informed that they will be free to terminate participation at any time during the study. The rights and welfare of participants will be protected by emphasizing to them that the quality of their medical care will not be adversely affected if they decline to participate in the study.

We are recruiting English-speaking and Spanish-speaking individuals for this study. Each participating dialysis clinic has in-clinic non-English interpretation coverage by a professional interpreter. The interpreter will interpret for Spanish-speaking patients while the Principal Investigator or other study staff consent patients for the study. If Spanish-speaking participants have questions outside of study visit times, the interpreter will provide language interpretation over the phone. In addition, one of our Research Assistants is Spanish-speaking.

13.4 PARTICIPANT AND DATA CONFIDENTIALITY

Study procedures and data collection will be performed after informed consent is obtained via patient signature on the IRB-approved consent form. All electronic information will be stored on a password-protected UNC computer (with secure, password and firewall-protected Department of Medicine server back-up) in the locked office of the study Principal Investigator and will be identifiably by study identification number only. Information linking the study identification number to the patient will be kept in a separate, password-protected database on the computer. Signed consent forms will be kept in a locked filing cabinet in the Principal Investigator's locked office. Initial paper records of study HD treatment data will be stored in a locked filing cabinet in the locked office of the Principal Investigator. Paper records will be destroyed (shredded and disposed in locked, shred bins) after verification of electronic data entry. Only the Principal Investigator and research assistant will have access to patient information with patient identifiers. No documents containing patient information with patient identifiers will be downloaded off of the secure Department of Medicine server onto personal computers.

13.4.1 RESEARCH USE OF STORED HUMAN SAMPLES, SPECIMENS OR DATA

One vial of stored blood will be maintained in UNC Kidney Center freezers (5th floor Burnett-Womack) until 12 months after study completion. Access to stored samples will be limited to study staff. Samples and data will be stored using codes assigned by the investigators. Data will be kept on password-protected secure Department of Medicine servers. Only study staff will have access to the samples and data. Study participants who request destruction of the sample prior to the 12 months after study completion date will be notified of compliance with such request and all supporting details will be maintained for tracking.

13.5 FUTURE USE OF STORED SPECIMENS

With the participant's approval and as approved by the IRB, de-identified biological samples will be stored in the UNC Kidney Center freezers (5th floor Burnett-Womack). After the study is completed, the de-identified, archived blood sample will be maintained for 12 months under the supervision of the PI, [name]. There will be no transfer of the specimens for use outside of the study. Potential additional laboratory testing (e.g. B-type natriuretic

peptide) relevant to this study may be performed. No genetic testing will be performed. The potential for additional laboratory testing on stored specimens will be listed in the IRB-approved consent form.

During the conduct of the study, an individual participant can choose to withdraw consent to have biological specimens stored for future use. However, withdrawal of consent with regard to biosample storage will not be possible after the study is completed.

